Appendix

1. [Apixaban Package Insert](https://packageinserts.bms.com/pi/pi_eliquis.pdf) (Version June 2018)
https://packageinserts.bms.com/pi/pi_eliquis.pdf
2. [Eliquis Medication Guide](https://packageinserts.bms.com/medguide/medguide_eliquis.pdf)
https://packageinserts.bms.com/medguide/medguide_eliquis.pdf
3. Informed Consent Form

Table. Amendments between original and final versions of the protocol

Section	Location in Protocol	Change from original to final version	Rationale for Change	IRB Approval Date
Study Inclusion criteria	Page 20	Added the following: "(Note: including post COVID-19 infection and post COVID-19 vaccination)"	We have clarified that COVID-19 and/or vaccination for COVID-19 may be considered as provoking factors for VTE.	December 20, 2021

Statistical Analysis Plan (SAP)

Randomized Controlled Trial of Extended-Duration Low-Dose Apixaban to
Prevent Recurrence in High-Risk Patients with Provoked Venous
Thromboembolism (HI-PRO Trial)

Date: 03/24/2025
(First and final version)

Study PI: [name], MS

Table of Contents

1. Study Overview.....	3
2. Specific Aims	3
3. Definitions	3
3.1 Target Population	3
3.2 Study Inclusion Criteria.....	4
3.3 Study Exclusion Criteria.....	4
4. Outcomes	4
4.1 Efficacy Outcomes.....	4
4.1.1 Primary Efficacy Outcomes.....	5
4.1.2 Secondary Efficacy Outcomes	5
4.2 Safety Outcomes	5
4.2.1 Principal Safety Outcome	5
4.2.2 Secondary Safety Outcome	5
5. Details of Randomization and Blinding.....	6
6. Statistical Plan	6
6.1 Power Calculation.....	6
6.2 Cohort Definition.....	7
6.2.1 Table. Analysis cohorts.....	8
6.3 Baseline Demographics and Clinical Comorbidities Description	9
6.4 Survival Analysis	9
6.4.1 Principal Analysis.....	9
6.4.2 Subgroup Analysis.....	10
6.5 Back-Up Methods if Proportional Hazard Assumption is Violated	10
6.6 Interim Analysis	10
6.7 Stopping for safety:.....	10
6.8 Stopping for futility:.....	11
6.9 Stopping for efficacy (superiority):.....	11

1. Study Overview

Patients who have experienced at least one persistent provoking factor following an initial provoked venous thromboembolism (VTE) are suspected to be at an increased risk of recurrence. However, it is still unclear whether extended-duration anticoagulation is beneficial for such patients. The HI-PRO randomized controlled trial conducted at Brigham and Women's Hospital (BWH) has been designed to investigate the safety and efficacy of extended-duration low-dose apixaban 2.5 mg twice daily for preventing recurrence in high-risk patients after initial provoked VTE.

2. Specific Aims

In this section, we provide an overview of the trial's specific aims. Based on the emerging evidence that provoked VTE patients may require extended-duration anticoagulation for secondary prevention, the apixaban 2.5 mg twice daily dose could be a critical addition to our armamentarium in those at high risk for recurrence at the transition of care from the acute to the chronic treatment phase. However, this hypothesis needs to be tested in a randomized clinical trial. We propose a single-center (BWH), randomized placebo-controlled trial conducted at to evaluate the impact of low-dose apixaban (2.5 mg twice daily) in a study population exclusively comprised of provoked VTE patients with at least one persistent provoking factor. We have the following study aims:

Specific Aim #1: To compare the 12-month recurrent symptomatic VTE in patients with provoked VTE and at least one enduring factor who are randomized to either apixaban (2.5 mg orally twice daily) as monotherapy or placebo after completing at least 3 months of therapeutic anticoagulation and who have a low risk of bleeding.

Specific Aim #2: To compare the 12-month ISTH major bleeding in patients with provoked VTE and at least one enduring factor who are randomized to either apixaban (2.5 mg orally twice daily) as monotherapy or placebo after completing at least 3 months of therapeutic anticoagulation and who have a low risk of bleeding.

3. Definitions

3.1 Target Population

The study is planned to enroll a total of 600 subjects at Brigham and Women's Hospital (BWH). The study design is a single center randomized controlled trial that will take place at BWH. The allocation ratio for the study is 1:1, meaning that half of the participants will be assigned to apixaban 2.5 mg twice daily, and the other half will be assigned to placebo for a duration of one year.

To ensure that the study enrolls the most appropriate participants, a set of detailed inclusion and exclusion criteria have been developed. These criteria are intended to identify individuals who are at high risk of recurrent VTE and are likely to benefit from extended-duration anticoagulation therapy without incurring a prohibitive risk of bleeding.

The allocation of treatments will be conducted by randomization procedures, ensuring that each participant has an equal chance of being assigned to the apixaban or placebo group. The study will be closely monitored for safety, and participants will be closely followed up throughout the study period to assess the efficacy and safety of the treatment. Below, we provide the detailed inclusion and exclusion criteria, which has been described.

3.2 Study Inclusion Criteria

The study is looking for men and women aged 18 years or older who have been objectively confirmed with provoked DVT and/or PE, and have been treated with standard therapeutic anticoagulant therapy for at least three months without symptomatic recurrence. Participants must have at least one enduring VTE risk factor, such as obesity, heart failure, chronic lung disease, chronic kidney disease, pregnancy, or use of hormonal therapies such as oral contraceptives, or chronic inflammatory/autoimmune disorder. They must be willing to provide written informed consent and have outpatient follow-up at BWH. Participants who have atherosclerotic cardiovascular disease may also be eligible for the study, with up to 35% in each study group having this condition as a qualifying persistent risk factor. The study also includes individuals who have experienced VTE post-COVID-19 infection and post-COVID-19 vaccination.

Eligible patients will be allowed to have multiple risk factors, and there will not be a limit as to how many of the above risk factors a subject may have. In addition, we will place no limit on the number of patients included with multiple risk factors. A study population with multiple risk factors is highly representative of the provoked VTE population and will provide the greatest generalizability of the study results to real-world clinical practice. Including patients with single and multiple persistent provoking risk factors will also facilitate enrollment. As noted, there is clinical and research equipoise regarding whether patients with a single or multiple persistent provoking VTE risk factors should receive extended duration thromboprophylaxis for secondary prevention.

3.3 Study Exclusion Criteria

The study excludes pregnant or breastfeeding women, women who are of child-bearing potential and unwilling or unable to use an acceptable method of birth control, and individuals with active cancer within the past 5 years or a contraindication to antithrombotic or antiplatelet therapy. The study also excludes those who require ongoing anticoagulant therapy, dual antiplatelet therapy, P2Y12 inhibition, or aspirin at a dose of > 81 mg daily. Other exclusion criteria include various medical conditions, such as severe thrombophilia, hemoglobin level < 9 mg/dL, platelet count < 100,000/mm³, serum creatinine level > 2.5 mg/dL, ALT or AST level > 2 times the upper limit of the normal range, or a total bilirubin level > 1.5 times the upper limit of the normal range. Additionally, individuals with a history of a platelet disorder, bleeding diathesis, or recent active bleeding, active severe hepatobiliary disease, or more than 6 months that have elapsed without taking an anticoagulant or low-dose aspirin are excluded. The study also excludes individuals with a known severe thrombophilia, life expectancy < 12 months or hospice care, prisoners, and individuals who are compulsorily detained for treatment of either a psychiatric or physical illness. Finally, individuals who are receiving concurrent non-FDA-approved or investigational agents or have received an investigational agent within the past 30 days prior to the first dose of study treatment are also excluded, as well as those who have a history of a severe hypersensitivity reaction to apixaban or require a medication that is contraindicated to be co-administered with apixaban.

4. Outcomes

Both safety and efficacy will be assessed in this trial. Outcome definitions are as follows:

4.1 Efficacy Outcomes

4.1.1 Primary Efficacy Outcomes

The primary efficacy outcome will be the time to first symptomatic, recurrent VTE, defined as the composite of fatal or nonfatal deep vein thrombosis and/or pulmonary embolism within 12 months from randomization. The primary efficacy outcome will be independently adjudicated by a Clinical Events Committee (CEC) blinded to assigned treatments. DVT is diagnosed as a newly non-compressible venous segment or segments on ultrasonography or a filling defect on computed tomographic (CT) venography, magnetic resonance (MR) venography, or contrast venography. PE is diagnosed based on new mismatched perfusion defect(s) on ventilation-perfusion scan, the presence of a new pulmonary artery filling defect on contrast-enhanced chest CT, a new finding of intraluminal filling defect on invasive pulmonary angiography, or evidence of PE at autopsy. Death due to causes other than DVT or PE will be considered a competing risk for this outcome.

4.1.2 Secondary Efficacy Outcomes

Secondary efficacy outcomes include the time to first occurrence of a composite of death due to cardiovascular causes, nonfatal myocardial infarction (MI), stroke or systemic embolism, chronic limb-threatening ischemia (CLTI), or coronary or peripheral ischemia requiring revascularization (major adverse cardiovascular events, including major adverse limb events) within 12 months, and the individual components of this outcome. An additional composite outcome will include all the components of the above composite of major adverse cardiovascular events as well as symptomatic VTE. A composite thrombotic outcome will be analyzed and will include symptomatic VTE, fatal or nonfatal myocardial infarction (MI), stroke/TIA or systemic embolism. The secondary efficacy outcomes will be independently adjudicated by a CEC blinded to assigned treatments. Non-cardiovascular death will be considered a competing risk.

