DVT is diagnosed as a newly non-compressible venous segment or segments on ultrasonography or a filling defect on computed tomographic (CT) venography, magnetic resonance (MR) venography, or contrast venography.

PE is diagnosed based on new mismatched perfusion defect(s) on ventilation perfusion scan, the presence of a new pulmonary artery filling defect on contrast-enhanced chest CT, a new finding of intraluminal filling defect on invasive pulmonary angiography, or evidence of PE at autopsy.

Secondary Efficacy Outcome

A secondary efficacy outcome will be the composite of death due to cardiovascular cause, nonfatal myocardial infarction (MI), stroke or systemic embolism, critical limb ischemia (CLI), or coronary or peripheral ischemia requiring revascularization (major adverse cardiovascular events, including major adverse limb events) at 12 months. The secondary efficacy outcome will be independently adjudicated by a blinded CEC review.

An acute MI is defined as the presence of at least 2 of the 3 following conditions (29):

- The detection of a rise and/or fall of cardiac biomarkers, with at least one of the values being elevated (preferably cardiac troponin [cTn] with at least one value above the 99th percentile upper reference limit) and with at least one of the following:
 - symptoms of myocardial ischemia
 - new (or presumably new) significant ST-segment/T-wave changes or left bundle branch block
 - development of pathological Q waves on ECG
 - new loss of viable myocardium or regional wall motion abnormality by imaging
 - identification of intracoronary thrombus by angiography or autopsy

An acute stroke is defined as a new, focal neurologic deficit of sudden onset, lasting at least 24 hours, not due to a readily identifiable nonvascular cause (i.e. brain tumor, trauma), as confirmed by a neurologist and neuroimaging (7). All strokes during the study will be assessed by imaging or autopsy, and classified as primary hemorrhagic, non-hemorrhagic, infarction with hemorrhagic conversion, or unknown, as defined by the American College of Cardiology.

- **Primary hemorrhagic:** a stroke with documentation on imaging (e.g., CT scan or magnetic resonance imaging) of hemorrhage in the cerebral parenchyma, or subarachnoid hemorrhage. Evidence of hemorrhagic stroke obtained from lumbar puncture, neurosurgery, or autopsy can also confirm the diagnosis.

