- **Non-hemorrhagic:** an ischemic focal neurological deficit (and not due to hemorrhage) that appears and is still partially evident at 24 hours.
- **Infarction with hemorrhagic conversion:** no evidence of hemorrhage on an initial scan, but found on a subsequent scan and is clinically relevant to the event, as determined by a neurologist.
- **Unknown type/no imaging performed:** the type of stroke could not be determined by imaging or other means (lumbar puncture, neurosurgery).

Cardiovascular death is defined as a death for which a definite non-cardiovascular cause (e.g. cancer) has not been identified. Uncertain causes of deaths are presumed to be cardiovascular unless proven otherwise.

Major adverse limb events include acute limb ischemia (ALI) and critical limb ischemia (CLI) (30). Acute limb ischemia is defined as limb-threatening ischemia which is confirmed by limb hemodynamics or imaging and leads to an acute vascular intervention (i.e. pharmacologic [heparin, thrombolysis], peripheral arterial surgery/reconstruction, peripheral angioplasty/stent, or amputation) within 30 days of onset of symptoms. In the absence of confirmation by limb hemodynamics or imaging, absent pedal pulses is acceptable as hemodynamic criterion for acute limb ischemia. If the event does not meet the definition for ALI it may be classified as

chronic limb ischemia, peripheral vascular intervention or other peripheral vascular hospitalization.

CLI is defined as continuing ischemic limb, foot or digit pain leading to hospitalization and intervention and not meeting the definition of ALI, or Fontaine 3 or 4 at baseline with peripheral intervention during the trial.

Peripheral vascular intervention is defined as peripheral vascular intervention not meeting the definition for ALI or CLI.

Additional Study Outcomes: Admission for heart failure will also be assessed at 12 months. Adherence to the twice-daily regimen of apixaban (and placebo) will be recorded as the total number of doses taken divided by the total number of doses prescribed. Adherence data will be recorded on patient-maintained drug diaries.

Clinical Endpoints Committee Adjudication of Study Outcomes

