Primary and secondary safety and efficacy outcome will be independently adjudicated by a Clinical Endpoints Committee (CEC) that is blinded with regards to the subject's treatment allocation (randomization). The CEC will include a chairperson and independent reviewers who are physicians with experience in vascular medicine and thrombosis. The CEC will adjudicate all index events (proximal DVT and/or PE). During the study period and the post-treatment observation period, the CEC will adjudicate all suspected occurrences/recurrences of venous or arterial thromboembolic events, deaths, and the following events of special interest: acute myocardial infarction, acute stroke, and thrombocytopenia. The CEC will also review all suspected episodes of bleeding, and categorize adjudicated bleeding as major, clinically relevant non-major, or minor bleeding. The Committee will be provided with all relevant documentation related to the events but will be blinded as to the subject's treatment allocation. The criteria and definitions of the study outcomes as well as the procedures followed by the Committee are described in this protocol.

Drug Accountability

Study drug and placebo will be physically stored at BWH in our Investigational Drug Pharmacy. Drug handling and dispensing will be accomplished through our BWH Investigational Drug Service. The Director of Pharmacy at BWH will oversee the Investigational Drug Service in this regard for the purposes of the clinical trial. Documentation of administration will be accomplished by our Electronic Health Record (EHR; EPIC) in addition to a patient drug diary, which is being kept to assess medication adherence. The Investigational Drug Service will collect empty study drug containers and unused drug via mail using prepaid labels that will be provided to the patient or courier as per Investigational Drug Service policy. We will perform drug accountability assessment when the drug containers are collected at each 3-month interval.

Follow-Up

Follow-Up Evaluation

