
Stroke/TIA (defined as a new, focal neurologic deficit of sudden onset, lasting at least 24 hours, not due to a readily identifiable nonvascular cause (i.e. brain tumor, trauma), as confirmed by a neurologist and neuroimaging.)
	
 Yes  No
 
If yes, date _____ / _____ / _____ MM DD YYYY
 
Confirmation (both must be present):
 
 By neurologist  By neuroimaging
 
TIA?  Yes  No
 
Stroke?  Yes  No
 
If yes, type of stroke:  Ischemic

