4.2 Safety Outcomes

4.2.1 Principal Safety Outcome

The principal safety outcome will be the time to first major bleeding within 12 months from randomization. Major bleeding is defined according to the International Society on Thrombosis and Haemostasis (ISTH) as overt bleeding that is associated with a decrease in the hemoglobin level ≥ 2 g/dL, leads to transfusion ≥ 2 units of packed red blood cells, occurs in a critical site, or contributes to death 1. The principal safety outcome will be independently adjudicated by a blinded CEC review. Non-hemorrhagic death will be considered a competing risk for this outcome.

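### The thrombotic composite in SAP 4.1.2 does not limit stroke to ischemic stroke, so as written a hemorrhagic stroke counts as a thrombotic efficacy event

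*Combined protocol and SAP*

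**What the plan says.** SAP 4.1.2 (Secondary Efficacy Outcomes) introduces an outcome that the protocol does not have: "A composite thrombotic outcome will be analyzed and will include symptomatic VTE, fatal or nonfatal myocardial infarction (MI), stroke/TIA or systemic embolism". It is separate from the MACE composite and from the composite of MACE plus VTE in the same section.

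The SAP gives no definition of stroke. The protocol does, under Secondary Efficacy Outcome. Each stroke is to be "classified as primary hemorrhagic, non-hemorrhagic, infarction with hemorrhagic conversion, or unknown", and the first of these classes is "a stroke with documentation on imaging (e.g., CT scan or magnetic resonance imaging) of hemorrhage in the cerebral parenchyma, or subarachnoid hemorrhage". The protocol section on adjudication by the Clinical Endpoints Committee (CEC) says where the outcome rules are found: "The criteria and definitions of the study outcomes as well as the procedures followed by the Committee are described in this protocol".

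Major bleeding in SAP 4.2.1 includes overt bleeding that "occurs in a critical site, or contributes to death". The case report form lists intracranial among the sites of a major bleed, and for a stroke it has the field "If yes, type of stroke".

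**The concern.** An outcome labelled thrombotic should collect events that an anticoagulant might prevent. Hemorrhagic stroke is an event that an anticoagulant might cause. The protocol takes that view itself: it names major bleeding as the foreseeable risk of apixaban and sets a stopping count of three unprovoked intracranial hemorrhages in the apixaban group.

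If hemorrhagic stroke is inside the thrombotic composite, benefit and harm are added together. A hazard ratio nearer to 1 could then mean less protection from thrombosis or more brain bleeding, and the reader could not tell which from the composite. The label would also misdescribe what was counted.

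**Working it through.** **Text check.**

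1. The stroke term in the thrombotic composite is unqualified (SAP 4.1.2).
2. The SAP has no stroke definition. The CEC section of the protocol refers to the protocol for outcome definitions, and the stroke definition there has four classes, one of them primary hemorrhagic.
3. No sentence in either document excludes that class from the thrombotic composite. By default it is included.
4. The reach of this default is limited. The bleed must be parenchymal or subarachnoid and must meet the stroke definition: a new sudden focal deficit lasting at least 24 hours, without a nonvascular cause such as trauma. Traumatic bleeds do not meet it, and isolated subdural or epidural bleeds would not obviously count.

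**Size.** The documents give no rate, event count or power for this composite, so there is no stated figure to reproduce. The following is an illustration under assumptions. It uses only the VTE part of the composite.

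Inputs from the protocol's Sample Size Calculation: 300 per arm, 6% on placebo, a 75% reduction and hence 1.5% on apixaban.

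- Placebo VTE events: 300 × 0.06 = 18.
- Apixaban VTE events: 300 × 0.015 = 4.5.
- Ratio with no hemorrhagic strokes: 4.5 / 18 = 0.25.
- Ratio with k hemorrhagic strokes on apixaban and none on placebo: (4.5 + k) / 18.
- k = 1 gives 5.5 / 18 = 0.31.

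The value of k is assumed. Larger values move the ratio further (k = 2 gives 0.36, k = 3 gives 0.42), but they are hard to support. The protocol background quotes all major bleeding in a trial of extended rivaroxaban as 0.4% on 10 mg and 0.3% on aspirin. If those rates are borrowed for 300 per arm, which is a further assumption because drug and comparator differ, they give 300 × 0.004 = 1.2 and 300 × 0.003 = 0.9 major bleeds at all sites. Even if every one were a hemorrhagic stroke, the ratio would be (4.5 + 1.2) / (18 + 0.9) = 5.7 / 18.9 = 0.30.

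Myocardial infarction, ischemic stroke, TIA and systemic embolism also belong to the composite. If a such events occur in each arm, the shift caused by k hemorrhagic strokes on apixaban is k / (18 + a). For k = 1 this is 1/18 = 0.056 when a = 0, and half that (1/36 = 0.028) when a = 18.

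**The case against.** The best counter-argument is that silence is not a rule. The outcome is called thrombotic, a blinded committee adjudicates it, and each stroke is typed. The protocol's stroke definition was written for the MACE composite, not for this one. A committee or analyst might therefore leave hemorrhagic strokes out without being told to. That is possible, but a label is not an event definition, and the only definition available includes the hemorrhagic class. If exclusion was intended, it should be stated.

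The counter-argument on consequence largely stands. This is one of several secondary composites, with no power calculation of its own. The rule applies equally to both arms. The expected direction is against apixaban, so it should not create a false claim of benefit. Stroke type and intracranial bleeding are recorded, so the events can be separated later.

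A reader might also infer three stronger points that the documents do not support.

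- *That leaving out acute limb ischemia (ALI) is an error.* The protocol says "Major adverse limb events include acute limb ischemia (ALI) and critical limb ischemia (CLI"). SAP 4.1.2 lists "chronic limb-threatening ischemia (CLTI), or coronary or peripheral ischemia requiring revascularization" and does not name ALI, but it describes that composite as one that includes major adverse limb events. Revascularized cases have a listed component there, and embolic cases may fit systemic embolism. The thrombotic composite omits chronic limb ischemia and revascularization as well, so it is consistently narrower. That is a design choice.
- *That the event is double-counted.* A hemorrhagic stroke may properly appear once in an efficacy composite such as MACE and once in major bleeding, because these are separate outcomes. The fault is its place in an outcome labelled thrombotic.
- *That the ratio would move to 0.42.* That needs three hemorrhagic strokes on apixaban, none on placebo and no other arterial events. Three is 1.0% of 300, which is 2.5 times the 0.4% quoted above for all major bleeding, and it equals the protocol's stopping count if the bleeds are unprovoked.

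**Conclusion.** The point holds for the stroke component. As written, the thrombotic composite includes primary hemorrhagic stroke by default and so mixes the drug's expected harm into a benefit outcome. The primary efficacy and principal safety outcomes are not affected.

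The size cannot be fixed from the documents. One hemorrhagic stroke on apixaban and none on placebo would take the VTE-only planning ratio from 0.25 to about 0.31, and less once other arterial events are counted. This rests on the planning rates, 300 per arm and an assumed count. The direction rests on bleeding being more likely on apixaban, which the protocol expects but does not quantify for stroke. It should be corrected because the definition is unclear and the correction is cheap, not because a large distortion has been shown.

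**What to change.** In SAP 4.1.2, define the stroke component of the thrombotic composite as non-hemorrhagic stroke or infarction with hemorrhagic conversion, using the protocol's classes. Include strokes of unknown type, and add a sensitivity analysis that excludes them. State that primary hemorrhagic stroke stays in the MACE composite and in major bleeding. Once it is out of the thrombotic composite, a death from hemorrhagic stroke needs a stated place there. SAP 4.1.2 names only non-cardiovascular death as a competing risk, so the same edit should make such a death a competing event.

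If treatment assignments are already unblinded, report the restricted composite beside the composite as now written, and label it a later clarification.

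Optional, for clarity only: name ALI in the component list of the MACE composite.

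The cost is a few sentences in the SAP. The protocol already requires stroke typing and the case report form has a field for it, so no new data are needed. The composite may lose a few events.
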